5.4.2 Discontinuation of Entire Study

AbbVie may terminate this study prematurely, either in its entirety or at any study site, for reasonable cause provided that written notice is submitted in advance of the intended termination. The investigator may also terminate the study at his/her site for reasonable cause, after providing written notice to AbbVie in advance of the intended termination. Advance notice is not required by either party if the study is stopped due to safety concerns. If AbbVie terminates the study for safety reasons, AbbVie will immediately notify the investigator by telephone and subsequently provide written instructions for study termination.

5.5 Treatments

5.5.1 Treatments Administered

Study drug will be provided as a sterile solution for SC injection, contained in pre-filled syringes containing adalimumab 40 mg/0.8 mL or matching placebo for adalimumab. The investigator or designee will subcutaneously administer study drug to the subject per the dosing schedule.

Double-Blind Period (Week 0 – Week 8)

Adalimumab 40 mg/0.8 mL or Placebo for Adalimumab 0.8 mL:

During the randomized double-blind treatment period, subjects will be randomized to one of two groups. Subjects randomized to adalimumab will receive blinded adalimumab

160 mg at Week 0, 80 mg at Week 2, and 40 mg at Week 4 and Week 6. Subjects randomized to placebo will receive matching placebo at Week 0 and Week 2, adalimumab 160 mg at Week 4, and adalimumab 80 mg at Week 6. At Week 8, all subjects will commence and 18-week OL period during which they will receive adalimumab 40 mg eow.

Open-Label Period (Week 8 – Week 26)

Adalimumab 40 mg/0.8 mL:

Starting at the Week 8 visit all subjects will receive one injection with 40 mg adalimumab and then eow until Week 26. If subject qualifies for dose escalation during the OL Period the subject may escalate to adalimumab 80 mg eow.

The duration of the study could be up to 39 weeks which includes a Screening Period of up to 35 days, 8 weeks double-blind treatment periods, an 18-week OL period, and a follow-up period 70 days from the last dose of study drug to obtain information on any new or ongoing AEs.

At or after Week 12, any subject who experiences inadequate response (defined below), may increase dose to open-label adalimumab 80 mg eow. If the subject has received open-label 80 mg eow therapy and continues to demonstrate inadequate response, they should be withdrawn from the study.

No dose will be given at the final visit (Week 26).

For the Purposes of Dose Escalation, Inadequate Response:

Crohn's disease activity index (CDAI) \geq 200 and at least one of the following criteria is met: an increase of at least 1 mg/L in level of high-sensitivity C-reactive protein (hs-CRP) from Baseline or an hs-CRP \geq 5 mg/L.

The hs-CRP results used to determine inadequate response should be the most recent available results. Assessment of inadequate response should include consideration by

the Investigator to rule out symptoms caused by reasons other than Crohn's disease related inflammation. The most recent hs-CRP value should first be compared to the most recent CDAI from the previous visit. Then the most recent hs-CRP value should be assessed in relation to CDAI calculated at the current visit. Dose changes are to only occur in accordance with the eow dosing schedule.

5.5.2 Identity of Investigational Products

The individual study drug information is presented in [Table 4](#).

Table 4. Study Drugs

Drug	Dosage Form	Device	Formulation	Manufacturer
Adalimumab	Parenteral	Pre-filled syringe	40 mg/0.8 mL solution for injection Adalimumab/Mannitol, Citric acid monohydrate, Sodium citrate, Disodium phosphate dihydrate, Sodium dihydrogen phosphate dihydrate, Sodium chloride, Polysorbate 80, Water for injections, Sodium hydroxide added as necessary to adjust pH	AbbVie
Placebo	Parenteral	Pre-filled syringe	0.8 mL solution for injection mannitol, Citric Acid monohydrate, Sodium citrate, Disodium phosphate dehydrate, Sodium dihydrogen phosphate dehydrate, Sodium chloride, Polysorbate 80, water for injections, Sodium Hydroxide added as necessary to adjust pH	AbbVie

5.5.2.1 Packaging and Labeling

Investigational product will be packaged separately in 0.8 mL syringe containing either adalimumab 40 mg/0.8 mL or matching placebo for adalimumab. Each dosing kit carton contains two pre-filled syringes to accommodate study design. The syringe and/or carton labels will minimally contain the information as required per country requirements.

All labels must remain affixed to study medication at all times, and should never be removed for any reason.

Detailed instructions and training for the administration of study drug supplies are provided in [Appendix E](#) and [Appendix F](#).

5.5.2.2 Storage and Disposition of Study Drug

Adalimumab pre-filled syringes are to be stored protected from light at 2° to 8°C/36° to 46°F. Study medication drug must not be frozen at any time. A storage temperature log is to be maintained to document proper storage conditions. The refrigerator temperature must be recorded (daily is recommended) on a temperature log to record proper function. Malfunctions or any temperature excursion must be reported to the Sponsor immediately. Study medication should be quarantined and not dispensed until AbbVie GPRD or AbbVie Temperature Excursion Management System (ATEMS), if applicable, deems the medication as acceptable.

All clinical supplies must be stored and locked in a secure place until they are dispensed for subject use or are returned to AbbVie.

Investigational products are for investigational use only and are to be used only within the context of this study.

5.5.3 Method of Assigning Subjects to Treatment Groups

All subjects will be assigned a unique identification number by the IRT system at the screening study visit. Subjects who meet the entry criteria in [Section 5.2.1](#) and [Section 5.2.2](#) will proceed to be enrolled into the study. Subjects who enter the study will be randomized at Baseline (Week 0) in a 1:1 ratio to receive adalimumab or placebo. The randomization will be stratified by Crohn's disease severity (CDAI \leq 300, $>$ 300) at Baseline (Week 0) and corticosteroid use at Baseline.

The sites will be provided with appropriate kit number(s) for drug-dispensing purpose for each subject by the IRT. Before the study is initiated, the access information for the IRT

system will be provided to each site. Study drug will be administered at the study visits summarized in [Table 1](#).

5.5.4 Selection and Timing of Dose for Each Subject

Subjects should take study medication as outlined in [Section 5.5.1](#).

If a subject should forget or miss their regularly scheduled visit for the injection of study medication on their regularly scheduled dosing date, they should return to the site to take the forgotten or missed injection as soon as they remember the dose was missed up to the day of their next scheduled dose. The subject should not administer two doses on the same day.

Doses not administered (e.g., not taken before next dose is scheduled), should be recorded as not taken in the source. The extra dose should remain full at the study site. The subject should resume their regular dosing schedule based on the first dosing date at Baseline (Week 0) and the site should obtain new study drug kit assignment from the IRT system.

5.5.5 Blinding

5.5.5.1 Blinding of Investigational Product

All AbbVie personnel with direct oversight of the conduct and management of the trial (with the exception of AbbVie Drug Supply Management Team) the Investigator, study site personnel and the subject will remain blinded to each subject's treatment throughout the blinded period of the study. The Interactive Response Technology (IRT) will provide access to blinded subject treatment information in the case of medical emergency.

In the event of a medical emergency in which the Investigator believes that knowledge of study drug treatment is required, every effort must be made to contact the AbbVie SDP ([Section 7.0](#)) prior to breaking the blind. The date and reason that the blind was broken must be conveyed to AbbVie and recorded on the appropriate eCRF.

5.5.6 Treatment Compliance

The investigator or his/her designated and qualified representatives will administer/dispense study drug only to subjects enrolled in the study in accordance with the protocol. The study drug must not be used for reasons other than that described in the protocol.

If the subject doses at home, the subject or their qualified designee will administer all doses of assigned study drug. Appropriate site staff will supervise the subject's administration of the study drug at required in-office study visits to ensure proper injection technique. In order to document compliance with the treatment regimen, the subject will be given a diary to record all injection dates and times. Compliance information will be documented on the appropriate eCRF. Subjects will be counseled on missed doses of medication. If the subject does not return the diary, IP boxes and sharp containers (when applicable), the site should question the subject and obtain as much information as possible as to the dosing of the study drug.

The information should be documented on the source documents as per "best recollection" and when possible, re-verified when the diary is returned before completing on the applicable eCRF page.

5.5.7 Drug Accountability

The Investigator or designee will verify that study drug supplies are received intact, at the appropriate temperature, and in the correct amounts. This will be accomplished by documenting the condition of the shipment, verifying the kit numbers in the package against the Proof of Receipt (POR) or similar document included with each drug shipment, and documenting this verification by signing and dating the POR or similar document. The original POR Note or similar document will be kept in the site files as a record of what was received.

In addition, an accurate running inventory of study drug will be kept by the site in the IRT system including date received, the lot number, box number(s), date dispensed, subject

number, drug expiration date, and the identification with date of the person dispensing the drug. All expired drug will be removed from refrigerated storage and placed under quarantine until such a time as it can be returned to AbbVie.

All empty Investigational Product (IP) boxes will be inventoried by the site and verified by the Monitor. Monitors and site staff will complete study medication accountability via study medication logs and empty IP at each visit. Once the monitor has verified drug accountability at the site, the site staff and monitor will document that the used pre-filled syringes have been destroyed, using appropriate biohazard precautions. Used Sharps containers should never be opened. After verification of drug accountability by the site staff and the monitor, used pre-filled syringes will be destroyed by the site. A copy of the destruction methodology should be maintained at the site's facility. All unused study drug must be inventoried, accounted for and returned to Depot for destruction. The IRT system will produce list of study drug being returned; the list should be enclosed with the shipment.

5.6 Discussion and Justification of Study Design

5.6.1 Discussion of Study Design and Choice of Control Groups

The study design was chosen to demonstrate the efficacy of adalimumab as induction and maintenance therapy for Crohn's disease. Subjects with active CD who meet all inclusion criteria and none of the exclusion criteria are eligible for this study. The specific subject population chosen was based on the unmet medical need for subjects with moderately to severely active symptoms plus evidence of active inflammation (as documented by hs-CRP).

The first 4 weeks of the double-blinded period will evaluate the efficacy of adalimumab (160/80 mg at Week 0/2) to induce clinical remission (CDAI < 150) at Week 4 compared to placebo. Recognizing the severe and debilitating nature of Crohn's disease and the associated suffering experienced by subjects, subjects randomized to placebo will receive induction with adalimumab 160/80 mg at Weeks 4/6 (subjects randomized to adalimumab will receive adalimumab 40 mg at Weeks 4 and 6 with matching placebo to retain

blinding). Beginning at Week 8, all subjects will receive open-label therapy with adalimumab 40 mg every other week. Rates of remission at Week 26 will be evaluated in subjects meeting the definition for response (reduction in CDAI \geq 70 points from Baseline) after induction therapy (determined at Week 8) and compared against a clinically meaningful remission rate obtained using the data from adult placebo from Western CD Study M02-404 (see Section 8.2 for details).

5.6.2 Appropriateness of Measurements

Standard pharmacokinetic, statistical, clinical, and laboratory procedures will be utilized in this study. All efficacy measurements in this study are standard for assessing disease activity in subjects with CD. All clinical and laboratory procedures in this study are standard and generally accepted.

5.6.3 Suitability of Subject Population

Subjects with active CD who meet all inclusion criteria and none of the exclusion criteria are eligible for this study. The specific subject population chosen was based on the unmet medical need for subjects with moderately to severely active CD in China who also have evidence of active inflammation (by hs-CRP).

5.6.4 Selection of Doses in the Study

The dose of adalimumab to be tested in the Chinese patient population is the same dose approved globally (US, EU, and Japan package labels) for patients with Crohn's disease and was selected based on similar pharmacokinetics in Chinese subjects observed in Study M14-232 as in studies conducted in Western subjects. The 160/80 mg induction dose was associated with the greatest efficacy in Study M02-403 and Study M14-232, and is the approved dose in the US, Japan, and one of the two approved doses in Europe. The 40 mg every other week maintenance dose is the approved dose in the US, EU, and Japan, and the 80 mg every other week dose for subjects with inadequate response is the same dose approved in Japan for subjects with inadequate response to 40 mg every other week maintenance dosing.

6.0 Complaints

A Complaint is any written, electronic, or oral communication that alleges deficiencies related to the physical characteristics, identity, quality, purity, potency, durability, reliability, safety, effectiveness, or performance of a product/device after it is released for distribution.

The investigational product in this trial contains both:

- Biologic compound(s) and
- Device component(s) (pre-filled syringe).

Complaints associated with any component of this investigational product must be reported to the Sponsor (Section 6.2.2). For adverse events, please refer to Sections 6.1 through 6.1.7. For product complaints, please refer to Section 6.2.

6.1 Medical Complaints

The investigator will monitor each subject for clinical and laboratory evidence of adverse events on a routine basis throughout the study. The investigator will assess and record any adverse event in detail including the date of onset, event diagnosis (if known) or sign/symptom, severity, time course (end date, ongoing, intermittent), relationship of the adverse event to study drug, and any action(s) taken. For serious adverse events considered as having "no reasonable possibility" of being associated with study drug, the investigator will provide an "Other" cause of the event. For adverse events to be considered intermittent, the events must be of similar nature and severity. Adverse events, whether in response to a query, observed by site personnel, or reported spontaneously by the subject will be recorded.

All adverse events will be followed to a satisfactory conclusion.

6.1.1 Definitions

6.1.1.1 Adverse Event

An adverse event is defined as any untoward medical occurrence in a patient or clinical investigation subject administered a pharmaceutical product and which does not necessarily have a causal relationship with this treatment. An adverse event can therefore be any unfavorable and unintended sign (including an abnormal laboratory finding), symptom, or disease temporally associated with the use of a medicinal (investigational) product, whether or not the event is considered causally related to the use of the product.

Such an event can result from use of the drug as stipulated in the protocol or labeling, as well as from accidental or intentional overdose, drug abuse, or drug withdrawal. Any worsening of a pre-existing condition or illness is considered an adverse event.

Worsening in severity of a reported adverse event should be reported as a new adverse event. Laboratory abnormalities and changes in vital signs are considered to be adverse events only if they result in discontinuation from the study, necessitate therapeutic medical intervention, meet protocol specific criteria (See Section 6.1.7 regarding toxicity management), and/or if the investigator considers them to be adverse events.

An elective surgery/procedure scheduled to occur during a study will not be considered an adverse event if the surgery/procedure is being performed for a pre-existing condition and the surgery/procedure has been pre-planned prior to study entry. However, if the pre-existing condition deteriorates unexpectedly during the study (e.g., surgery performed earlier than planned), then the deterioration of the condition for which the elective surgery/procedure is being done will be considered an adverse event.

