4.3 Sample Size

The Week 4 primary efficacy endpoint is defined as the proportion of subjects achieving CDAI < 150. Based on the adalimumab China Phase 2 CD Study M14-232 (no placebo group in that study), the remission rate at Week 4 was 67% in the adalimumab 160/80 mg treatment group and 40% in the adalimumab 80/40 mg treatment group. In Western CD Study CLASSIC I (Study M02-403), the Week 4 remission rate was 40% in the adalimumab 160/80 mg treatment group and 8% in the placebo group among subjects with elevated hs-CRP at baseline (hs-CRP \geq 3 mg/L). Considering that the placebo effect in China Phase 3 study will potentially be higher than the Western placebo rate, and the treatment effect in the adalimumab 160/80 mg treatment group will potentially be lower than the China Phase 2 CD study, the assumption of remission rates at Week 4 for this study is 24% and 47% for placebo and the adalimumab 160/80 mg treatment groups, respectively, with the expected treatment difference of 23%. A sample size of 100 subjects per arm (total 200 subjects) will provide power of 90% to detect a 23% treatment difference in the primary efficacy endpoint between the adalimumab 160/80 mg treatment group and placebo (1:1 randomization ratio), using two-sided Fisher's exact test at a 0.05 significance level.

If the overall Week 8 response rate is 50%, it is expected that approximately 100 subjects who are Week 8 responders will enter the open-label maintenance period and comprise the analysis population for Week 26 endpoints. Based on the observed Week 26 remission rate in Western CD Study M02-404 in anti-TNF naïve subjects with elevated CRP at baseline (hs-CRP \geq 3 mg/L) who responded to adalimumab induction therapy (52% [34/66]) for the adalimumab 40 mg EOW treatment group the sample size of 100 subjects will allow \geq 99% power to detect remission rate at Week 26 of 52% against a clinically meaningful remission rate of 30% using one-sample Exact test at a two-sided 0.05 significance level. The remission rate of 30% was obtained using the upper bound of the 95% CI of the adult placebo rate from the Western CD Study M02-404 in the same subgroup of subjects.

Prior to the completion of Study M14-233 study enrollment, assessment of the sample size based on the blinded data (overall event rate at Week 4) will be conducted.

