11.0 Safety Analysis

11.1 General Considerations

Safety analyses will include reporting of adverse events, laboratory, and vital sign measurements. Safety analyses will be carried out using the Safety set for the DB placebo controlled period (Week 0 to Week 4), and will be carried out using the Any Adalimumab set for the DB/OL period of Any Adalimumab (the entire study on or after the first dose of adalimumab up to 70 days after the last dose of adalimumab, or the date subjects initiate adalimumab therapy not supplied in the context of Study M14-233). The safety analyses results through Week 4 will be presented using two treatment groups (i.e., ADA160/80 versus placebo). The safety analysis on the Any Adalimumab set will be presented for all the subjects as one adalimumab treatment group.

Comparisons between active treatment and placebo groups will be performed for the DB placebo controlled period using the safety analysis set. The safety variable will be summarized by treatment according to the treatment a subject actually received. The differences between treatment group and placebo in safety parameters will be evaluated using two-sided tests at the significance level of 0.100.

For the any adalimumab analysis Set, only summary statistics will be provided for adalimumab treatment.

Missing safety data will not be imputed.

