11.2 Analysis of Adverse Events

11.2.1 Treatment-Emergent Adverse Events

Treatment-emergent AEs will be summarized separately for the DB placebo-controlled period and for the DB/OL period of Any Adalimumab.

Treatment-emergent AEs during placebo-controlled DB period are defined as events that begin or worsen either on or after the first dose of study drug and up to the first dose of

study drug at Week 4, or within 70 days after the last dose of study drug, or the date subjects initiate adalimumab therapy not supplied in the context of Study M14-233, for subjects who discontinued prior to Week 4. Treatment-emergent AEs during DB/OL period of Any Adalimumab are defined as events that begin or worsen either on or after the first dose of adalimumab in DB or OL period, and within 70 days after the last dose of study drug, or the date subjects initiate adalimumab therapy not supplied in the context of Study M14-233.

An overview of treatment-emergent AEs, including AEs of special interest such as adverse events leading to death and adverse events leading to early termination, AEs by Medical Dictionary for Drug Regulatory Activities (MedDRA version 20.0 or later) preferred term and system organ class, AEs by maximum relationship to study drug, and AEs by maximum severity will be summarized by number and percentage.

The number and percent of subjects experiencing treatment-emergent adverse events will be summarized for the following adverse event categories. Comparisons of the percent of subjects experiencing an adverse event between adalimumab and placebo during the DB placebo controlled period will be performed using Fisher's exact tests. Only P values < 0.100 when rounded to three digits will be presented.

- Any treatment-emergent adverse event.
- Any treatment-emergent adverse event with a Reasonable Possibility of being related to study drug by the investigator.
- Any treatment-emergent severe adverse event.
- Any treatment-emergent serious adverse event.
- Any treatment-emergent adverse event leading to discontinuation of study drug.
- Any treatment-emergent adverse event leading to death.
- Any treatment-emergent adverse event of special interest.
- Any deaths.

Adverse events with missing or unknown relationship to study drug will be categorized as having a reasonable possibility of being study drug-related. Adverse events with missing or unknown severity will be categorized as severe.

Treatment-emergent adverse events will be summarized as follows:

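### Worsening of Crohn's disease counts as an adverse event, so four all-event rows of the placebo-controlled safety comparison mix lack of efficacy with drug harm and can understate an adalimumab excess

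*Protocol*

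**What the plan says.** Protocol Section 6.1.1.1: "Any worsening of a pre-existing condition or illness is considered an adverse event". No exception is made for the disease under study. Under Section 6.1.1.2 a hospital admission of any length makes an event serious, so a flare that leads to admission is a serious adverse event.

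Safety is part of the primary objective (Protocol Section 4.0, SAP Section 4.1). SAP Section 11.1 makes the between-arm comparison on the "Safety set for the DB placebo controlled period (Week 0 to Week 4"). After that there is no control: "For the any adalimumab analysis Set, only summary statistics will be provided for adalimumab treatment". Differences are "evaluated using two-sided tests at the significance level of 0.100".

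SAP Section 11.2.1 applies Fisher's exact test to a list of overview rows: any event, related, severe, serious, leading to discontinuation, leading to death, of special interest, and deaths. It adds that "Only P values < 0.100 when rounded to three digits will be presented". For subjects who stop before Week 4, the same section counts events up to 70 days after the last dose, or until they start adalimumab from outside the study.

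For efficacy, SAP Section 4.3 says that "the assumption of remission rates at Week 4 for this study is 24% and 47% for placebo and the adalimumab 160/80 mg treatment groups".

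**The concern.** A worsening of Crohn's disease enters the any-event row. It also enters the severe, serious or discontinuation row if it meets that row's condition. If the drug works, such events should be more frequent on placebo, while drug-related events should be more frequent on adalimumab. Adding the two narrows the difference that these four rows are meant to show. Because only P values below 0.100 are printed, a diluted excess may appear with no P value at all.

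At stake is the reading of the summary safety rows from the one randomised comparison. No planned comparison gives total, severe, serious or discontinuation-related events without disease worsening.

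**Working it through.** **1. Reproduce the plan's own figure.** The documents state no power for safety. The nearest stated figure is 90% for the primary endpoint (24% vs 47%, 100 per arm, two-sided Fisher's exact test at 0.05). Enumerating both binomial distributions gives 90.7%, so the method agrees with the plan. The same enumeration at 0.10 is used below.

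**2. Inputs.**
- From the documents: 100 per arm; Fisher's exact test; two-sided 0.10; non-remission at Week 4 of 1 − 0.24 = 76% on placebo and 1 − 0.47 = 53% on adalimumab.
- Assumed, because the documents give no adverse event rates: other events in 30% (placebo) and 40% (adalimumab); a fraction f of non-remitters with a recorded worsening, taken as 5%, 10% and 20%; worsening independent of other events.

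**3. Formula.** Rate in the any-event row = 1 − (1 − other) × (1 − worsening), where worsening = f × 0.76 on placebo and f × 0.53 on adalimumab.

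For f = 20%, worsening is 15.2% vs 10.6%:
- Placebo: 1 − 0.70 × 0.848 = 40.6%
- Adalimumab: 1 − 0.60 × 0.894 = 46.4%
- Difference: 46.36 − 40.64 = 5.7 points

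**4. Results.**

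| f | Worsening, placebo vs adalimumab | Any-event row | Difference (points) | Power at 0.10 |
|---|---|---|---|---|
| none | 0 vs 0 | 30.0% vs 40.0% | 10.0 | 37% |
| 5% | 3.8% vs 2.7% | 32.7% vs 41.6% | 8.9 | 31% |
| 10% | 7.6% vs 5.3% | 35.3% vs 43.2% | 7.9 | 25% |
| 20% | 15.2% vs 10.6% | 40.6% vs 46.4% | 5.7 | 17% |

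**5. How much is mere overlap.** If worsening were equal at 10.6% in both arms, the difference would be 10 × 0.894 = 8.9 points and power 31%. In the f = 20% case, then, about 1 point of the 4.3-point loss would arise without any imbalance in worsening. The rest comes from the imbalance.

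**6. Serious row, with every rate assumed.** Other serious events 1% vs 6% and disease-related serious events 5% vs 2% give 1 − 0.99 × 0.95 = 6.0% and 1 − 0.94 × 0.98 = 7.9%. The difference falls from 5 points to 1.9, and power from 44% to 8%. This shows what can happen in a row with few events. It is not a forecast.

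**7. Other assumed rates.** With other events 20% vs 35%, power without worsening is 72%. It becomes 54% with worsening of 5% vs 2%, 33% with 10% vs 3%, and 9% with 20% vs 5%. The direction is the same and the size depends on the assumption.

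**The case against.** Several points on the other side are sound.

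- **Not every row is affected.** A reader might infer that the overview has no row free of Crohn's worsening. It has one: the special-interest row is built from the list in SAP Section 11.2.2, which does not contain worsening of Crohn's disease. Intestinal stricture and perforation are on the list and can be complications of the disease, but a flare as such is not.
- **Infections are not hidden.** A reader might also infer that an excess of infections could disappear. Section 11.2.2 summarises infection, serious infection, tuberculosis, malignancy, allergic reaction and others separately, and a flare cannot dilute those counts.
- **The related row is largely protected.** Worsening enters it only where causality is judged a reasonable possibility, or is missing or unknown and so classed as related.
- **Non-remission is not worsening.** Subjects enter with CDAI 220 to 450, so one who is unchanged or partly improved at Week 4 is a non-remitter without an event. The 76% and 53% serve only as a base for an assumed fraction.
- **The window is short.** The steroid taper starts at Week 4, so taper-related flares fall mostly outside it. Against this, subjects who stop early can contribute events for up to 70 days after their last dose.
- **Power is low anyway.** In the main illustration it is only 37% with no worsening, and at f = 5% the loss is about 1 point of difference and 6 points of power.
- **The data can be re-cut.** SAP Section 11.2.1 plans a by-subject listing and a preferred-term table with subject numbers, so a total without Crohn's worsening can be counted afterwards. That count would carry no planned test, and its terms would be chosen after unblinding. The plain preferred-term table cannot supply the total by subtraction, because one subject can have both kinds of event.

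**Conclusion.** The point holds for four rows: any, severe, serious and leading to discontinuation. They can understate an adalimumab excess in the placebo-controlled comparison. That the two effects actually cancel is a stronger reading, which the documents do not support: they give no rate for worsening or for any other adverse event, and the loss is small if few subjects worsen. Under the stated assumptions (other events 30% vs 40%, worsening in 5% to 20% of expected non-remitters, independence), a 10-point difference shows as 8.9 to 5.7 points and power falls from 37% to between 31% and 17%. The planned test is valid for what it counts, and no data go uncollected. What is missing is a pre-specified version of these totals without disease worsening. Priority is low to moderate.

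**What to change.** In SAP Section 11.2.1:

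- Repeat the any, severe, serious and leading-to-discontinuation rows, with their Fisher comparisons for the placebo-controlled period, excluding worsening of Crohn's disease.
- Define the exclusion by a short preferred-term list fixed before database lock and unblinding. State whether complications such as stricture and perforation are on it.
- Show worsening of Crohn's disease as its own row.
- Keep all existing rows unchanged, so that nothing is removed from the all-event account.

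The cost is a few lines of SAP text, the term list and some extra table rows. Adverse event collection, conduct and sample size do not change.
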